#### 3.1 OVERALL STUDY DESIGN AND FLOW CHART

This is a multinational, multicenter, Non-Interventional, study of patients with symptomatic, aggressive, sporadic, unresectable, locally advanced/metastatic MTC, treated with vandetanib 300 mg/once daily and with a RET mutation positive or negative status including RET mutation negative patients who never received vandetanib (as many patients as possible, with no restriction on the numbers of RET mutation negative patients). Patients will be either prospectively followed, or in addition, patients with symptomatic, aggressive, sporadic, unresectable, locally advanced/metastatic MTC and with a RET mutation negative status, will be allowed to enter the study retrospectively.

Twenty to twenty-five vandetanib RET mutation positive and 20 to 25 vandetanib RET mutation negative patients will be enrolled in the study.

For prospective patients (patients with RET mutation positive or negative): study visits will include a screening visit and/or enrollment visit, where the eligibility of the patient will be confirmed, plus additional follow-up visits:

- For effectiveness measurement purposes, Investigators are strongly recommended to perform a complete disease assessment (biomarkers, symptoms and imaging) at least every 6 months according to both site normal clinical practice and International MTC guidelines (4, 5). Response Evaluation Criteria in Solid Tumors (RECIST) 1.1 will be used as a base for calculation for disease assessment.
- For patients prescribed with vandetanib, prescription frequency and safety assessments should be done according to specifications in the Summary of Product Characteristics (SmPC) (see [Appendix B](#)).

Patients will be followed until objective progression or until the end of study (whichever occurs first).

For retrospective patients (only MTC patients with RET mutation negative status):

Data collection reporting time points will include a baseline time point before the start of their treatment for MTC (vandetanib or another treatment) where the eligibility of the patient will be confirmed, plus all subsequent time points that may be available in the patient file.

[figure not shown]
- Complete disease assessment (biomarkers, symptoms, and imaging) according to both site normal clinical practice and international MTC guidelines will be reported (4, 5). RECIST 1.1 will be used as a base for calculation for disease assessment.

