- Diagnosis of MTC could be as early as 1995-2000. The centers will search their databases for the prevalent MTC patients and review the records to consider recruitment using 2010 as a cutoff, without any limitation for the date of diagnosis. The prescription frequency of vandetanib or any other treatment for MTC should be reported. All efforts will be made to report safety assessments according to specifications in the SmPC, based on the data that will be available in the patient charts (see [Appendix B](#)).

Data collection and reporting will be performed until objective progression, or until the end of study (whichever occurs first). For all patients end of study is defined as 14 months after the last prospective patient has been enrolled in the study and when at least 10 events in each treatment group have been observed. If all patients have progressed prior to 14 months after the last patient is recruited, the study will stop.

The minimum follow-up time period of 14 months for prospective arm (not retrospective) is appropriate because approximately 80% of patients who had an objective response in a pivotal Phase III study achieved their response within 14 months of starting vandetanib (3).

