**Table 4 - Study plan**

Time	Screening/Enrollment visit or baseline time point	Follow-up visits for prospective patients or follow-up time points for retrospective patients
Obtain Informed Consent a	X	-
Inclusion/exclusion criteria assessment	X	-
Patient Characteristics, including RET status b	X	-
Disease assessment c	X	X
Treatment information	X	X
Safety information	X	X
Laboratory d	X	X

*a* Waiver for retrospective patients

*b* For retrospective patients: RET mutation negative status may have been performed before or after start of the treatment of medullary thyroid cancer (MTC) (Vandetanib or another treatment).

*c* Disease assessment should be consistent (same time frequency and method) within a site across the study for prospective patients, but not necessarily for retrospective patients.

*d* Potassium, creatinine, calcium, magnesium and thyroid stimulating hormone (TSH) will be collected at baseline, at 1, 3, 6 and 12 weeks after starting treatment and every 3 months for one year.

RET= Rearranged during transfection

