### 4.2 INCLUSION CRITERIA

The patient population that will be included in the NIS must fulfill all the following criteria:

- I 01. Signed informed consent for prospective patients. No need for signed informed consent for retrospective patients (waiver).
- I 02. Male or female aged 18 years or above for prospective patients. No age restriction for retrospective patients.
- I 03. Histological diagnosis of MTC (for retrospective patients [prevalent MTC patients] diagnosis could be as early as possible, without any limitation for the date of diagnosis).
- I 04. Patients with symptomatic and aggressive sporadic MTC, who have unresectable, locally advanced/metastatic disease. (The factors considered by the Investigator to determine a patient's disease to be symptomatic and aggressive will be recorded in the electronic case report form [eCRF], allowing for missing data for the retrospective patients).
- I 05. Measurable disease:
  - Assessment confirmed within the 12 weeks previous to start of treatment, and
  - Defined according to RECIST 1.1: at least 1 lesion, not irradiated, that can be accurately measured as  $\geq 10$  mm in the longest diameter (except lymph nodes which must have short axis  $\geq 15$  mm) with computed tomography (CT) or magnetic resonance imaging (MRI) and which is suitable for accurate repeated measurements. Measurable lesions with calcifications should not be assessed as target lesions unless no other measurable lesion is available.

Known definite RET mutation status (definition according to [Section 3.2](#)). The status should be:

- For prospective patients prescribed with vandetanib: positive or negative.
- For prospective patients not prescribed with vandetanib: negative.
- For retrospective patients prescribed or not prescribed with vandetanib: negative.

- For prospective patients: RET mutation status must be determined from a tumor sample obtained within 18 months prior to enrollment. It is strongly recommended that a tissue sample obtained within 6 months prior to enrollment is used. For retrospective patients: RET mutation negative mutation status could have been determined within 18 months before or after start of treatment (with vandetanib or another drug). In case of retrospective patient treated with another drug, the patient should have been treated with vandetanib at any time.

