#### 4.3 EXCLUSION CRITERIA

- E 01. Current or planned inclusion/participation in a clinical trial, not applicable for retrospective patients.
- E 02. Patients already receiving vandetanib or who have received vandetanib for their MTC before the study first visit, not applicable for retrospective patients.
- E 03. Contraindications according to the vandetanib SmPC, not applicable for retrospective patients and for patients who do not receive vandetanib:
- A) Patients with a QTc interval over 480 msec:
    - Congenital long QT syndrome
    - Concomitant use of vandetanib with the following medicinal products known to also prolong the QT interval and/or induce Torsades de pointes: Arsenic, cisapride, erythromycin intravenous, toremifene, mizolastine, moxifloxacin, Class IA and III antiarrhythmics
  - A) Currently pregnant or breast-feeding, not applicable for retrospective patients.
  - B) Hypersensitivity to the active substance or to any of the excipients, not applicable for patients who do not receive vandetanib.
  - C) Severe renal impairment: creatinine clearance <30 mL/minute calculated by Cockcroft-Gault formula, not applicable for patients who do not receive vandetanib (See [Appendix D](#)).
  - D) Serum bilirubin greater than  $1.5 \times$  the upper limit of reference range (ULRR), not applicable for patients who do not receive vandetanib.
  - E) Potassium, magnesium or calcium outside the normal laboratory range, not applicable for patients who do not receive vandetanib.

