### **9.3.3 Deaths**

All deaths (both cancer-related and other) that occur during the study up to 60 days after the last dose received must be reported as a SAE. In the event of death, the patient will be considered as having completed the study.

All dead patients will be considered for the retrospective data collection, with no exception.

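### A retrospective RET-negative patient may qualify on a RET test up to 18 months after baseline, so PFS on that side of the RET comparison includes time in which survival was required

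*Protocol*

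**What the plan says.** Retrospective entry is open only to RET mutation negative patients (protocol sections 3.1 and 4.2). Four pieces of text meet here:

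- **Test window.** Section 4.2 says a retrospective patient's status "could have been determined within 18 months before or after start of treatment". Footnote b of Table 4 repeats that "RET mutation negative status may have been performed before or after start of the treatment" and gives no limit.
- **Baseline.** Section 3.1 sets a "baseline time point before the start of their treatment for MTC (vandetanib or another treatment") and says eligibility is confirmed at that point.
- **Prospective patients.** Their RET status must be known for enrolment (sections 4.2 and 7.1), and exclusion E 02 keeps out "Patients already receiving vandetanib or who have received vandetanib for their MTC before the study first visit, not applicable for retrospective patients".
- **Analysis.** Objective F (section 2) compares PFS between RET-positive and RET-negative patients on vandetanib. Section 13.3.2 plans a Kaplan-Meier plot of PFS by RET status, with medians. The protocol gives no explicit PFS start date. The pre-treatment baseline is the only anchor it offers.

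**The concern.** If the qualifying result can come after baseline, eligibility cannot be confirmed at baseline, and the interval between the two is not ordinary follow-up. Someone who starts treatment and dies, or leaves care, before being tested does not appear in the data. Those who do appear generally had to survive that interval. A Kaplan-Meier curve counted from baseline treats them as at risk throughout, which biases PFS upward.

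The bias falls on one side. RET-positive patients in this study enter prospectively, with eligibility settled at the start of vandetanib, so they carry no such interval. The amendment was written to supply confirmatory data in RET-negative patients, so an upward bias in that group is the direction that matters most. By August 2018 only 8 RET-negative patients had been enrolled, against a target of 20 to 25. Without further prospective recruitment, 12 to 17 of the study's own RET-negative patients would be retrospective.

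**Working it through.** **The plan's own figure.** The only sample-size figure is Table 1, on objective response rate. 0.35 ± 1.96 × 0.4770/√n gives 14.1–55.9% (n = 20), 16.3–53.7% (n = 25) and 17.9–52.1% (n = 30), as printed. It does not concern PFS and is unaffected.

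**Inputs from the documents** (Appendix B, SmPC section 5.1, unless stated):
- test up to 18 months after start (section 4.2);
- median PFS m of 30.5 months (vandetanib arm, predicted) or 19.3 months (placebo arm, used as a pessimistic value);
- 9 of 73 PFS events on vandetanib were deaths without progression, so f = 0.1233;
- median overall survival of 81.6 months (vandetanib arm).

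**Assumptions, not in the documents:** exponential PFS with rate λ = ln 2/m; a constant death rate μ after progression, set so that median overall survival is 81.6 months; test timing unrelated to outcome; three patterns of test timing. PFS in RET-negative patients is unknown, so the two medians serve as a range.

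**Step 1, probability of being alive at a test d months after start:**

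A(d) = e^(−λd) + (1 − f) λ [e^(−μd) − e^(−λd)]/(λ − μ)

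For m = 30.5, λ = 0.02273, and matching overall survival gives μ = 0.01571. At d = 18, A = 0.6643 + 0.8767 × 0.02273 × (0.7536 − 0.6643)/(0.02273 − 0.01571) = 0.918. When test times are spread, A is the average over d; a test before start counts as 1.

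**Step 2, the naive median.** A patient whose PFS exceeds 18 months is alive at any test up to month 18. Beyond month 18 the naive curve is therefore the true curve divided by A, and the naive median is m × [1 + log2(1/A)]. With A = 0.918 this is 30.5 × 1.1234 = 34.3 months.

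| RET test timing | A, true median 30.5 | Naive median | A, true median 19.3 | Naive median |
|---|---|---|---|---|
| Uniform, −18 to +18 months | 98.2% | 31.3 | 97.6% | 20.0 |
| Uniform, 0 to 18 months | 96.4% | 32.1 | 95.2% | 20.7 |
| All at month 18 | 91.8% | 34.3 | 89.8% | 22.3 |

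A simulation of 1,000,000 patients agrees within 0.1 month. The shift is 0.7 to 3.8 months. Pooling retrospective patients tested uniformly over −18 to +18 months with the 8 prospective ones gives about 31.0 (true 30.5) and 19.7 to 19.8 (true 19.3).

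**Step 3, sensitivity.** With a median overall survival of 40 months (an assumption standing for short survival after progression), the naive medians are 32.5 to 40.8 and 20.5 to 25.3. If testing happened only in progression-free patients, they are 34.6 to 48.5 and 23.2 to 37.3.

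**Step 4, what delayed entry does.** Letting patients enter the risk set at the later of start and test recovers the truth when test times are spread: 30.4 to 30.6 and 19.3. If everyone is tested at month 18, it cannot recover the curve before month 18. It also drops patients who progressed before the test, a share of 1 − P(progression-free at test)/P(alive at test):
- true median 30.5: 1 − 91.0/98.2 = 7%, 1 − 82.0/96.4 = 15%, 1 − 66.4/91.8 = 28%;
- true median 19.3: 1 − 86.8/97.6 = 11%, 1 − 73.6/95.2 = 23%, 1 − 52.3/89.8 = 42%.

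**Step 5, the start date matters too.** The baseline may precede another drug. Section 4.2 adds: "In case of retrospective patient treated with another drug, the patient should have been treated with vandetanib at any time". For such a patient, time from the other drug to vandetanib is also required survival if the clock starts at the other drug. That sentence also sits badly with section 3.1, which admits patients never given vandetanib.

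**The case against.** **The analysis plan may settle this.** The start date and delayed entry are commonly set there, and that document is not shown. This stands as far as it goes: their absence from the protocol is not the point. The after-start window, the pre-treatment baseline and the confirmation of eligibility at that baseline are protocol text, and they do not fit together.

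**Dead patients are included.** Section 9.3.3 says "All dead patients will be considered for the retrospective data collection, with no exception". That removes the need to be alive when data are collected, not when the RET test is done. Section 7.1 does allow testing of stored tissue, so a test after death but inside the window would remove the requirement for that patient. Hence patients who die untested generally, not always, cannot enter.

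**Groups are reported separately.** Section 13.3 promises results for prospective, pivotal-study and retrospective patients as well as pooled. This may help a reader notice a distortion, but it corrects neither the retrospective nor the pooled curve, and the prospective RET-negative group is small. Table 2 shows a retrospective column for RET-positive patients too, but sections 3.1 and 4.2 admit none.

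**Stronger readings that the text does not support.** A reader might infer that patients had to be progression-free at the test, which gives the largest figures in step 3. Nothing requires that: progression before the test is in the chart and counts. A reader might also infer long guaranteed survival from section 3.1: "The centers will search their databases for the prevalent MTC patients and review the records to consider recruitment using 2010 as a cutoff". It does not say alive in 2010, and what the cutoff applies to is undefined. The years 1995–2000 are diagnosis dates, not baselines. First authorisation was 17 February 2012, so marketed vandetanib starts fall after 2010. Overall survival, where such an effect would be largest, is not a listed study variable.

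**Conclusion.** The point holds in a limited form. The rule requires survival to the RET test, on the RET-negative side only, and a Kaplan-Meier curve counted from the pre-treatment baseline includes that time. With pivotal-study medians the overstatement of median PFS is about 1 to 4 months, near the lower end if tests are spread evenly before and after the start. This rests on exponential times, test timing unrelated to outcome, and the inference that PFS is counted from that baseline. The shift grows if survival after progression is short or testing favours progression-free patients. It could reverse if progression prompts testing. The size does not undermine the study, but the bias is systematic, one-sided and inexpensive to examine.

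**What to change.** In section 13.3.2 (and the analysis plan):

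1. State the PFS start date: first vandetanib dose, or the start of the index treatment for patients not treated with vandetanib.
2. Add a sensitivity analysis of PFS limited to retrospective patients whose RET result is dated on or before that start.
3. Add a second sensitivity analysis in which retrospective patients enter the risk set at the later of the start date and the RET result date. Report how many progressed before the test and are therefore dropped.

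In section 3.1, reconcile the statement that eligibility is confirmed at baseline with the after-start window in section 4.2.

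The date of the RET assay is already collected (section 8.2). The cost is fewer patients and wider intervals in both sensitivity analyses. Delayed entry is better kept as a sensitivity analysis than made the main one: from perhaps 12 to 17 retrospective patients it would drop about 7 to 23% with spread test times, and 28 to 42% if all were tested at month 18. It is also valid only if test timing is unrelated to progression.

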#### 4.3 EXCLUSION CRITERIA

- E 01. Current or planned inclusion/participation in a clinical trial, not applicable for retrospective patients.
- E 02. Patients already receiving vandetanib or who have received vandetanib for their MTC before the study first visit, not applicable for retrospective patients.
- E 03. Contraindications according to the vandetanib SmPC, not applicable for retrospective patients and for patients who do not receive vandetanib:
- A) Patients with a QTc interval over 480 msec:
    - Congenital long QT syndrome
    - Concomitant use of vandetanib with the following medicinal products known to also prolong the QT interval and/or induce Torsades de pointes: Arsenic, cisapride, erythromycin intravenous, toremifene, mizolastine, moxifloxacin, Class IA and III antiarrhythmics
  - A) Currently pregnant or breast-feeding, not applicable for retrospective patients.
  - B) Hypersensitivity to the active substance or to any of the excipients, not applicable for patients who do not receive vandetanib.
  - C) Severe renal impairment: creatinine clearance <30 mL/minute calculated by Cockcroft-Gault formula, not applicable for patients who do not receive vandetanib (See [Appendix D](#)).
  - D) Serum bilirubin greater than  $1.5 \times$  the upper limit of reference range (ULRR), not applicable for patients who do not receive vandetanib.
  - E) Potassium, magnesium or calcium outside the normal laboratory range, not applicable for patients who do not receive vandetanib.

## **5 WITHDRAWAL OF PATIENTS**

### **5.1 CRITERIA FOR WITHDRAWAL**

Patients may be withdrawn from the NIS at any time. Specific reasons for withdrawing a patient from this NIS are:

1. Voluntary withdrawal by the patient who is at any time free to withdraw his/her participation in the NIS, without prejudice to further treatment (not applicable for retrospective patients).
2. Incorrect enrollment (inclusion/exclusion criteria are not fulfilled).
3. Inclusion in a clinical trial at any time during the study (not applicable for retrospective patients).

Discontinuation of the patient treatment is not a criterion for withdrawal from the study. In this case, the patient can continue in the study, until death, loss to follow-up, or end of study.

### **5.2 PROCEDURES FOR WITHDRAWAL**

For prospective patients: patients who withdraw should be asked about the reason(s) for their withdrawal. No specific procedures after withdrawal are required per study but continuation of patient assessment and treatment according to routine clinical practice.

No further data will be collected on prospective patients following withdrawal from the study.

Prospective patients who were not included (eg, for restrictive inclusion/exclusion criteria) or withdrawn from the study (eg, withdrawn due to AE but continuation of assessment and treatment according to routine practice) will still be considered for the retrospective data collection: if they meet the inclusion criteria for the retrospective data collection, the same patient ID will be used in the study database and the patient will be classified as retrospective patient for data analyses.

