## **9.2 RECORDING OF ADVERSE EVENTS**

### **9.2.1 Time period for collection of adverse events**

The AEs listed below will be collected throughout the study for prospective patients and retrospectively for retrospective RET mutation negative patients (based on data available in the patient charts), from informed consent form (ICF) signature (or start of vandetanib for retrospective patients where no ICF is required) until the end of the study follow-up period. For patients who discontinue or have discontinued (retrospective patients) the treatment with vandetanib before the end of the study follow-up period, AEs will be collected up to 60 days after the last dose received. Serious AEs occurring in the follow-up period should be reported to the Sponsor in the usual manner (see [Section 9.3.1](#)).

1. All SAEs
2. All AEs that led to discontinuation, interruption or modification of vandetanib dose
3. All events of diarrhea or dehydration, regardless of seriousness and severity
4. Abnormal results in ECG data, including heart rate and QT when clinically significant

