### **9.2.3 Variables**

The following variables will be collected for each AE:

- AE (verbatim)
- The date when the AE started and stopped
- Intensity
- Whether the AE is serious or not
- Investigator causality rating against the vandetanib (yes or no)
- Action taken with regard to vandetanib
- AE caused volunteer's withdrawal from study (yes or no)
- Outcome

In addition, the following variables will be collected for SAEs:

- Date AE met criteria for an SAE
- Date Investigator became aware of SAE
- AE is serious due to (specify reason)
- Date of hospitalization
- Date of discharge
- Probable cause of death
- Date of death
- Autopsy performed
- Causality assessment in relation to any medication
- Description of AE

The following intensity ratings will be used:

- Mild (awareness of sign or symptom, but easily tolerated)
- Moderate (discomfort sufficient to cause interference with normal activities)
- Severe (incapacitating, with inability to perform normal activities)

It is important to distinguish between seriousness and severity of AEs. Severity is a measure of intensity whereas seriousness is defined by the criteria in [Section 9.1.2](#). An AE of severe intensity needs not necessarily be considered serious. For example, nausea that persists for several hours may be considered severe nausea, but not a SAE. On the other hand, a stroke that results in only a limited degree of disability may be considered a mild stroke but would be a SAE.

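### Section 5.2 uses an adverse event as its example of study withdrawal, against 5.1, 6.1 and 7.2, and the follow-up that this ends can be recovered only for RET-negative patients

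*Protocol*

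**What the plan says.** Section 5.1 of the protocol opens with "Patients may be withdrawn from the NIS at any time". Under "Specific reasons for withdrawing a patient from this NIS are" it names three: the patient's own choice, incorrect enrollment, and entry into a clinical trial. It then adds that "Discontinuation of the patient treatment is not a criterion for withdrawal from the study".

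Sections 6.1 and 7.2 follow included patients until death, loss to follow-up or end of study. Section 3.1 stops at objective progression or end of study. None of these names an AE as an exit.

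Section 5.2 says: "No further data will be collected on prospective patients following withdrawal from the study". Its next paragraph gives as an example of a withdrawn prospective patient one "withdrawn due to AE but continuation of assessment and treatment according to routine practice". Such patients "will still be considered for the retrospective data collection" if they meet its criteria, keep their ID, and are then analysed as retrospective patients. Sections 3.1 and 4.2 limit the retrospective part to RET-negative patients.

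For patients who stop vandetanib before follow-up ends, Section 9.2.1 says "AEs will be collected up to 60 days after the last dose received". The AE form in Section 9.2.3 has a yes/no item for whether the event led the patient to leave the study, and a separate item for the action taken with vandetanib.

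**The concern.** The example in Section 5.2 describes someone who is still assessed and treated at the site. The chart goes on filling, but the study stops reading it because of toxicity. A site that takes the example as guidance would end follow-up that Sections 5.1, 6.1 and 7.2 require, and would lose AEs that Section 9.2.1 wants collected.

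The loss would not be even. A RET-negative patient with toxicity can be picked up again from the chart, although under a different group label. A RET-positive patient has no such route. Whether outcomes after toxicity are seen then depends on RET status, and Objective F (Section 2) compares progression-free survival (PFS) by RET status. The planned groups are 20 to 25 patients, so two or three lost patients would show.

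**Working it through.** **1. The texts side by side**

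| Question | 5.1, 6.1, 7.2 | 5.2 |
|---|---|---|
| Is an AE a reason to leave the study? | Not listed in 5.1; no AE exit in 6.1 or 7.2 | Used as the example of withdrawal |
| What if treatment stops? | The patient can stay in the study | Not addressed |
| When does data collection end? | Death, loss to follow-up or end of study (6.1, 7.2) | At withdrawal, unless the patient re-enters retrospectively |

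Section 5.2 also pulls against itself: collection ends at withdrawal, yet the same patients are considered for retrospective collection.

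**2. Who can be recovered**

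The amendment rationale counts 34 patients enrolled as of 2 August 2018.

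- RET-positive: 26/34 = 76%, no retrospective route under Sections 3.1 and 4.2.
- RET-negative: 8/34 = 24%, route open if the criteria are met.

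**3. The plan's own precision figure**

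Table 1 uses p ± 1.96 × SD/√n with p = 0.35 and SD = √(0.35 × 0.65) = 0.4770.

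- n = 20: ± 20.9 points, 14.1% to 55.9%
- n = 25: ± 18.7 points, 16.3% to 53.7%
- n = 30: ± 17.1 points, 17.9% to 52.1%

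All three rows reproduce. The table has no allowance for withdrawal.

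**4. How many patients**

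The protocol gives no rate of study withdrawal for AEs. The nearest figure is in Appendix B, Section 5.1: 28 of 231 vandetanib patients in Study D4200C00058 stopped treatment for an AE, 28/231 = 12.1%. Assume, as an upper case, that each such patient also left the study:

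- 20 × 0.1212 = 2.4
- 25 × 0.1212 = 3.0
- 26 × 0.1212 = 3.2 (RET-positive patients enrolled)
- 8 × 0.1212 = 1.0 (RET-negative patients enrolled, recoverable)

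The lower case is 0.

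**5. Effect on precision**

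With Table 1's formula and the remaining patients, the half-width goes from 20.9 to 22.3 points (20 down to 17.6 patients) or from 18.7 to 19.9 points (25 down to 22.0).

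**6. Effect on the RET-positive response rate**

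Table 3 gives an objective response rate (ORR) of 52% in patients with a documented RET mutation, which is 13 of 25. Section 13.3 leaves patients with missing data out of percentages, so a patient withdrawn before an evaluable follow-up scan could leave the denominator. If three do:

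- none of the three would have responded: 13/22 = 59.1%, a shift of +7.1 points
- all three would have responded later: (13 − 3)/22 = 10/22 = 45.5%, a shift of −6.5 points

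The shift can go either way.

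**The case against.** The case against is substantial, and much of it stands.

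- **The sentence is a recovery clause.** It describes patients who have already left, so that their data can be retrieved; it does not tell sites to withdraw anyone for an AE. A reader might infer that the response, PFS and AE data of these patients are simply lost. The documents do not support that: nothing discards what was collected before withdrawal, and RET-negative patients who qualify can be recovered. What remains is the unrecovered follow-up of RET-positive patients. Section 9.3.3 considers all deceased patients for retrospective collection, and the shell of Table 2 has a RET-positive retrospective column, but neither lifts the RET-negative requirement of Sections 3.1 and 4.2.
- **The list in 5.1 is not expressly closed.** Patients may leave at any time, and one who chooses to leave because of an AE falls under the first reason. This softens the conflict with 5.1. It does not reconcile the example with 6.1 and 7.2, which have no AE exit.
- **The 12.1% is not a withdrawal rate.** It is a treatment-discontinuation rate from another study, and 5.1 itself separates the two. It serves only as an assumed upper case.
- **A fixed direction of bias might be inferred**, with the response rate inflated and PFS too favourable. That needs an assumption that withdrawn patients do worse. The documents give no outcome or hazard after withdrawal, so no PFS figure is offered here, and the ORR range runs both ways.
- **The benefit comes late.** No new prospective patients were included after 30 June 2017, and this text is dated 21 June 2019. Early withdrawals in those enrolled will already have happened.
- **The AE-form item might be blamed too.** It only records an event, and it is the item that most directly identifies the patients affected. It should stay.

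**Conclusion.** The point holds as a conflict of text with a limited but uneven consequence. Section 5.2 treats an AE as an example of study withdrawal and ends collection there; Sections 5.1, 6.1 and 7.2 point the other way, and the 60-day window of 9.2.1 would be cut short. Because only RET-negative patients can re-enter, follow-up lost after toxicity depends on the factor compared in Objective F.

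The size is 0 to about 3 patients in a RET-positive group of 20 to 26. The upper end rests on two assumptions: that the pivotal study's 12.1% applies here, and that every such patient leaves the study. The ORR range of 45.5% to 59.1% around 52% further assumes that all three leave the denominator and are all of one kind. Either shift is well inside the 18.7-point half-width that Table 1 gives at n = 25 for a 35% rate. The reason to act is the dependence on RET status and the very low cost of repair, not a demonstrated bias.

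**What to change.** In Section 5.2, delete the AE example. State that an AE, including one that leads to stopping vandetanib, does not by itself end study follow-up. The patient stays in the prospective group and is followed as Sections 5.1, 6.1 and 7.2 say, unless the patient chooses to withdraw (the first reason in 5.1).

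Keep the study-withdrawal item in Section 9.2.3 and use it to list, by RET status, any prospective patients already withdrawn for an AE. No new item is needed for AEs that stop treatment, since the item on action taken with vandetanib can already capture them.

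The cost is one wording change and one extra listing. No visits are added, because the patients in the example remain in routine care. The change protects only follow-up still to come and cannot recover data already lost.
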